## **1 DOCUMENT HISTORY**

| Version                 | Date | Change to previous version |
|-------------------------|------|----------------------------|
| Final 1.0 30MAY2019 Nil |      | Nil                        |

This document is confidential and proprietary to Sponsor and EA and for restricted circulation and access only. No part of it may be transmitted, reproduced, published or used by any person/s without prior written authorization.

Version No.: Final 1.0

Page 6 of 38

Sponsor Study No: SPI-1005-251

Sponsor Name: Sound Pharmaceuticals, Inc.

ECRON ACUNOVA

NLS Study Code: SPI -1005 -251

Short Title of Study: SPI-1005-251 (Sound Pharmaceuticals, Inc)

## **2** ABBREVIATIONS

| ABBREVIATIONS      | DEFINITION   |
|--------------------|--|
| AE                 | Adverse Event  |
| AE(DAE)            | Discontinuation of the study due to Adverse Events       |
| ATC                | Anatomical Therapeutic Chemical Classification           |
| AUC 0-t | Area under the curve time 0 to time t                    |
| Bid                | Twice-daily dosing                                       |
| BMI                | Body Mass Index  |
| CBC                | Complete Blood Count                                     |
| CFR                | Code of Federal Regulations                              |
| C max   | Maximum concentration                                    |
| CRF                | Case Report Form   |
| CRO                | Contract Research Organization                           |
| CV                 | Coefficient of Variation                                 |
| dB                 | decibel, 1/10th of a Bel-measure of ratios on a logscale |
| dBHL               | dB Hearing Level   |
| EXP                | Exponential  |
| GCP                | Good Clinical Practice                                   |
| G.Mean             | Geometric Mean   |
| Hz                 | Hertz—unit of measure for frequency                      |
| IQR                | Inter Quartile Range                                     |
| ICH                | International Conference on Harmonization                |
| LCMS               | Liquid Chromatography-Mass Spectrometry                  |
| mg                 | milligram  |
| MD                 | Meniere's disease  |
| MedDRA             | Medical Dictionary for Regulatory Activities             |
| Max                | Maximum  |
| Min                | Minimum  |
| NA                 | Not Applicable   |
| PI                 | Principal Investigator                                   |
| РК                 | Pharmacokinetics   |

#### **Confidentiality Statement**

ECRON ACUNOVA

Sponsor Study No: SPI-1005-251

Sponsor Name: Sound Pharmaceuticals, Inc.

Version No.: Final 1.0

Page 7 of 38

NLS Study Code: SPI-1005-251

Short Title of Study: SPI-1005-251 (Sound Pharmaceuticals, Inc)

| By mouth Pure-Tone Audiometry |
|-------------------------------|
| Pure-Tone Audiometry          |
|                               |
| First Quartile                |
| Third Quartile                |
| Serious Adverse Event         |
| Statistical Analysis System   |
| Standard Deviation            |
| Subject Identification Code   |
| Signal-to-Noise Ratio         |
| Sound Pharmaceuticals, Inc.   |
| Square Root                   |
| Tinnitus Functional Index     |
| Tinnitus Loudness             |
| Temporary Threshold Shift     |
| Vertigo Symptoms Scale        |
| Words-in-Noise Test           |
|                               |

This document is confidential and proprietary to Sponsor and EA and for restricted circulation and access only. No part of it may be transmitted, reproduced, published or used by any person/s without prior written authorization. 9

Statistical Analysis PlanECRON ACUNOVA
Sponsor Study No: SPI-1005-251Version No.: Final 1.0Page 8 of 38Sponsor Name: Sound Pharmaceuticals, Inc.

NLS Study Code: SPI -1005 -251 Short Title of Study: SPI -1005 -251 (Sound Pharmaceuticals, Inc)

## **3 DOCUMENTS**

This statistical analysis plan is based on the study protocol SPI-1005-251, version 1.00 dated 21AUG2017.

# **4** INTRODUCTION

This Statistical Analysis Plan (SAP) is based on the relevant sections of study protocol and includes also the Tables, Listings and Figures (TLF) Specifications. The purpose of the SAP is to describe in more detail how the analyses are to be performed and presented. It quotes the relevant statements directly from the protocol, but it does not give a full description of study design etc.

The TLF Specifications specify the output to support the analysis. The TLF Specifications are considered as a guideline for producing the output.

The SAP will be finalized prior to database lock or any unblinding of study team members.

The objectives of this Phase 2b, randomized, double-blind, Placebo-controlled study are to demonstrate the safety and efficacy of SPI-1005 for the treatment of Meniere's disease.

## **5 STUDY OBJECTIVES**

### 5.1 Primary Objectives

- > To determine the Safety of SPI-1005 treatment in adults with Meniere's disease.
- To determine the Efficacy of SPI-1005 with the following clinically validated methods and measures (responder analysis):
  - Primary pure-tone audiometry assessment (250, 500 or 1000 Hz): Improvements from baseline of ≥10 dB at 1 frequency
  - Secondary pure-tone audiometry assessments (250, 500 or 1000 Hz): Improvements from baseline of ≥10 dB at 2 adjacent frequencies or ≥20 dB at 1 frequency
  - Primary Words-in-Noise Test assessment (0-35): Improvements from baseline of ≥10%
  - Secondary Words-in-Noise Test assessments (0-35): Improvements from baseline of ≥20% or ≥4 words
  - Tinnitus Functional Index (TFI):  $(0-100) \ge 10$  pt. reduction from baseline
  - Tinnitus Loudness: Q#2 of TFI:  $(0-10) \ge 2$  pt. reduction from baseline
  - Vertigo Symptom Scale (0-60):  $\geq 6$  pt. reduction from baseline

The responder analysis from each method and measure will be compared between treatment groups for significance.

- The efficacy of SPI-1005 treatment in adults with Meniere's disease will be based on:
  - Improvement in sensorineural hearing loss using pure-tone audiometry at 250, 500, or 1000 Hz; or

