**NCT Number: 03325790** 

# **1 PROTOCOL SUMMARY**

# 1.1 Synopsis

[figure not shown]
| SPI-1005-251: CLINICAL TRIAL SYNOPSIS |   |  |  |  |  |
|---------------------------------------|---|--|--|--|--|
| Title                                 | A PHASE 2b, RANDOMIZED, DOUBLE-BLIND, PLACEBO-
CONTROLLED STUDY TO EVALUATE THE SAFETY AND
EFFICACY OF SPI-1005 IN MENIERE'S DISEASE  |  |  |  |  |
| Study                                 | The primary objective of this Phase 2 study is to determine the:  |  |  |  |  |
| Objective(s)                          | • Safety of SPI-1005 treatment in adults with Meniere's disease.  |  |  |  |  |
|                                       | • Efficacy of SPI-1005 will be determined by the following clinically significant methods and measures (responder analysis):  |  |  |  |  |
|                                       | 
 
> Pure tone audiometry (≥30 dBHL at 250, 500 or 1000 Hz)
 
≥10 dB improvement from baseline
 
> Words in Noise Test (0-35)
 
  |  |  |  |  |
|                                       | 
 
≥10 % increase from baseline
 
➤ Tinnitus Functional Index (TFI) (0-100)
 
   |  |  |  |  |
|                                       | $\geq$ 10 pt. reduction from baseline   |  |  |  |  |
|                                       | 
 
Tinnitus Loudness: Q#2 of TFI (0-10)
 
2 pt. reduction from baseline
 
   |  |  |  |  |
|                                       | 
 
Vertigo Symptom Scale (0-60)
 
26 pt. reduction from baseline
 
  |  |  |  |  |
|                                       | 
 
The responder analysis from each method and measure will be compared between treatment groups for significance.
 
Efficacy of SPI-1005 treatment in adults with Meniere's disease based on 
 
Improvement in sensorineural hearing loss using pure tone audiometry at 250, 500, or 1000 Hz; or
 
Word recognition score using WIN testing at 24, 20, 16, 12, 8, 4 and 0 SNR; or
 
 
 
 |  |  |  |  |
|                                       |   |  |  |  |  |
|                                       |   |  |  |  |  |
|                                       | • Improvement in the Tinnitus Functional Index (TFI); or  |  |  |  |  |
|                                       | • Improvement in Tinnitus Loudness (TL); or   |  |  |  |  |

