| Inclusion
Criteria                 | 
 
Adult male and female patients, 18-75 years of age at the time of enrollment.
 
Diagnosis of probable or definitive Meniere's disease by AAO-HNS 1995 criteria (Section 12.1, APPENDIX I).
 
Two of three active symptoms including vertigo or disequilibrium, fluctuating hearing loss, or tinnitus within the 3 months prior to study enrollment.
 
Hearing loss of ≥30 dBHL at either 250, 500 or 1000 Hz.
 
Voluntary consent to participate in the study.
 
Male subjects that are willing to use condoms throughout the study period and 90-days following study completion even if not fertile.
 
Females of childbearing potential should either be sexually inactive (abstinent) for 14 days prior to screening and throughout the study or be using one of the following acceptable birth control methods: 
 
IUD in place for at least 3 months prior to study; or
 
Barrier method (condom or diaphragm) with spermicide for at least 14 days prior to screening through study completion; or
 
Stable hormonal contraceptive for at least 3 months prior
 
 
 
   |  |  |  |

| SPI-1005-251: CLINICAL TRIAL SYNOPSIS |  |  |  |  |
|---------------------------------------|--|--|--|--|
|                                       | 
 
to study and through study completion; or
 
Surgical sterilization (vasectomy) of partner at least 6 months prior to study enrollment.
 
Females of non-childbearing potential should be surgically sterile (bilateral tubal ligation with surgery at least 6 months prior to study enrollment, hysterectomy, or bilateral oophorectomy at least 2 months prior to study) or be at least 1 year since last menses.
 
 |  |  |  |
| Exclusion
Criteria                 |  |  |  |  |
| Study Duration                        | Estimated duration of 12 months  |  |  |  |
| Participant
Duration               | Participation for each study participants will be approximately 8 to 12 weeks across 4 clinic visits.  |  |  |  |
| Dose &
Regimen                     | Subjects will receive either SPI-1005 or matching placebo for 28 days.
Treatment will be taken orally BID. Doses include 200 mg or 400 mg
of ebselen or matching placebo in capsule form. Two week supplies
will be provided on Clinic Visit 1 and 2.   |  |  |  |

| SPI-1005-251: CLINICAL TRIAL SYNOPSIS |   |  |  |  |
|---------------------------------------|---|--|--|--|

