of treatment, and 28 days after treatment. Hearing thresholds (HL) will be determined using puretone audiometric (air conduction) testing at 250, 500, 1000, 2000, 3000, 4000, 6000, and 8000 Hz, bilaterally. In addition, bone conduction testing with masking will be conducted if the air conduction threshold is >15 dBHL at 250, 500, 1000, 2000, or 4000 Hz. Bone conduction testing will only be performed at screening and in the affected ear (>15 dBHL). A word recognition test using the Wordsin-Noise Test (WINT) at 24, 20, 16, 12, 8, 4, and 0 Signal-to-Noise ratio (SNR) will be used to evaluate hearing.

Following completion of informed consent process and baseline assessments, the study participants will be evaluated by the investigator for enrollment eligibility. Participants that meet enrollment criteria will be randomized and assigned a Subject Identification Code from the list of Subject Identification Codes. The Subject Identification Code must be carefully matched to the study drug before the study drug is dispensed at Clinic Visits 1, and 2.

A general diagram of the study design is provided in Figure 1.

This document is confidential and proprietary to Sponsor and EA and for restricted circulation and access only. No part of it may be transmitted, reproduced, published or used by any person/s without prior written authorization.

Version No.: Final 1.0

Page 11 of 38

A ECRON ACUNOVA

Sponsor Study No: SPI-1005-251

Sponsor Name: Sound Pharmaceuticals, Inc.

NLS Study Code: SPI-1005-251 Short Title of Study: SPI-1005-251 (Sound Pharmaceuticals, Inc) Screen for Screen participants (n=168 estimate) by inclusion and exclusion criteria Eligibility including history and review of systems Estimated Excluded (n=48) Did not meet I/E criteria (n=25) Declined to participate (n=13) Other reasons (n=10) Clinic Visit 1 Informed consent process, perform baseline assessments, confirm Day -28 to 1 eligibility, randomize, complete enrollment by providing study drug. Clinic Visit 2 Day 14 Perform protocol required assessments. Day 28 Clinic Visit 3 Perform protocol required assessments. Day 56 Clinic Visit 4 Final Assessments

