#### 6.2.1 Primary Parameter

- Efficacy of SPI-1005 will be determined by the following clinically significant methods and measures (responder analysis):
- ➤ Pure-tone audiometry assessment (250, 500 or 1000 Hz): Improvements from baseline of ≥10 dB at 1 frequency
- ▶ Words-in-Noise Test assessment (0-35): Improvements from baseline of  $\geq 10\%$ 
  - Tinnitus Functional Index (TFI) (0-100) ≥ 10 pt. reduction from baseline

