#### 8.3.1.1 Pure-Tone Audiometry

Pure-tone audiometry (PTA) will be measured at visit 1, visit 3 and visit 4.

Both the actual ear value and calculated change from baseline PTA data will be summarized by visits and treatment groups.

PTA data will be analyzed with a mixed-effects model for repeated measures, and a post-hoc Bonferroni correction analysis with significance set to 0.05. The calculated change of PTA data will be calculated by the difference of the actual ear value at baseline and the actual ear value at each visit post baseline. The primary assessment of PTA data will consider a  $\geq 10$  dBHL improvement from baseline as a clinically relevant response (only low frequency: 250, 500, 1000 Hz). The secondary assessments of PTA data will consider an improvement from baseline of  $\geq 10$  dBHL at two adjacent frequencies or  $\geq 20$  dBHL at one frequency as clinically relevant responses (only low frequency: 250, 500, 1000 Hz). The final processed data will be analyzed using a chi-square test or Fisher's Exact test to assess the improvement between treatment groups.

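### The SAP's primary PTA responder rule omits the protocol's ≥30 dBHL condition and names no ear, so a 10 dB retest shift at a frequency with normal baseline hearing counts as a response

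*SAP*

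**What the plan says.** **Protocol, 1.1 Synopsis.** Under the study objectives, the audiometric responder measure is headed "Pure tone audiometry (≥30 dBHL at 250, 500 or 1000 Hz", and the response is "≥10 dB improvement from baseline". The inclusion criteria use the same level: "Hearing loss of ≥30 dBHL at either 250, 500 or 1000 Hz". Neither entry names an ear.

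**SAP, statements of the primary rule.** None of the three has a baseline threshold or names an ear:
- 5.1: "Primary pure-tone audiometry assessment (250, 500 or 1000 Hz): Improvements from baseline of ≥10 dB at 1 frequency"
- 6.2.1: "Pure-tone audiometry assessment (250, 500 or 1000 Hz): Improvements from baseline of ≥10 dB at 1 frequency"
- 8.3.1.1: a 10 dB gain is taken as "improvement from baseline as a clinically relevant response (only low frequency: 250, 500, 1000 Hz"

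**SAP, ears.** Section 6.1 plans "audiometric (air conduction) testing at 250, 500, 1000, 2000, 3000, 4000, 6000, and 8000 Hz" in both ears. Section 8.3.1.1 states: "Both the actual ear value and calculated change from baseline PTA data will be summarized by visits and treatment groups". It does not say which ear's value is meant. An affected ear is mentioned only in 6.1, for bone conduction at screening.

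**SAP, deviations.** Section 9 sets the protocol objective, with its 30 dBHL text, beside SAP wording without it, and gives no reason.

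**The concern.** PTA response is one of five primary responder measures. Eligibility needs only one low frequency at ≥30 dBHL, so a patient's other low frequencies may be normal. Under the SAP rule a 10 dB shift at one of those makes a responder, although the stated aim is improvement in sensorineural hearing loss. Each extra site adds a chance to respond through measurement error. Under blinded randomisation this raises the rate equally in every arm and narrows the treatment difference.

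The undefined ear is a second gap. Two programmers could follow the text and produce different primary results: affected ear, either ear, or each ear as its own row. PTA is measured at visits 3 and 4, and no visit is named for the responder test. These choices should not be open once treatment codes are known.

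**Working it through.** **1. The plan's own figure.** SAP 7.6 calls 40 per group adequate to show a 50% improvement in a symptom by responder analysis. It gives no placebo rate and no power, so the figure cannot be reproduced. Read as a relative gain (×1.5), power at 40 per arm is 10% for a placebo rate of 10% and 64% for a rate of 50%. Read as 50 percentage points, it is above 99%. The power figures below therefore use a stated assumption.

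**2. Sites that could qualify at one visit.**
- One ear: 3 frequencies, so 3 sites.
- Either ear: 2 × 3 = 6 sites.
- A ≥30 dBHL floor in one ear: 1 to 3 sites in a patient whose qualifying frequency is in that ear.

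**3. Chance response with no true change.** Assumptions, none in the documents: thresholds in 5 dB steps and a retest-difference SD of 5 to 7 dB. With rounding, a recorded gain of 10 dB needs an underlying difference of at least 7.5 dB.

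Per site, q = 1 − Φ(7.5/SD):
- SD 5: 1 − Φ(1.50) = 6.7%
- SD 7: 1 − Φ(1.07) = 14.2%

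For k independent sites the chance is 1 − (1 − q)^k. For example, SD 5 and k = 3 gives 1 − 0.933³ = 18.7%. The correlated case (0.5 within an ear, 0.2 between ears) comes from simulating 400,000 patients.

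**4. Power.** Inputs: n = 40 per arm (SAP 7.6), two-sided 0.05 (SAP 7.1), and an assumed true response in 30% of patients who would not respond by chance. With chance rate f, placebo p0 = f and active p1 = f + 0.30(1 − f). Let p̄ be their mean.

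Power = Φ{[(p1 − p0)√n − 1.96√(2p̄(1 − p̄))] / √(p0(1 − p0) + p1(1 − p1))}

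Worked case, f = 0.067:
- p1 = 0.347 and p̄ = 0.207
- numerator 0.280 × 6.325 − 1.96 × 0.573 = 0.647
- denominator 0.538
- power Φ(1.20) = 88.6%

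| Sites | SD | Correlation | Chance rate f | Power |
|---|---|---|---|---|
| 1 | 5 | – | 6.7% | 88.6% |
| 1 | 7 | – | 14.2% | 74.5% |
| 3 | 5 | yes | about 15% | about 72% |
| 3 | 5 | none | 18.7% | 66.1% |
| 3 | 7 | yes | about 29% | about 49% |
| 3 | 7 | none | 36.9% | 39.5% |
| 6 | 5 | yes | about 27% | about 53% |
| 6 | 5 | none | 33.9% | 43.0% |
| 6 | 7 | yes | about 47% | about 30% |
| 6 | 7 | none | 60.1% | 20.2% |

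Lowering the SD to 4 dB and raising the correlation among all sites to 0.7 brings the chance rates down to about 3%, 7% and 10% for 1, 3 and 6 sites.

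**5. Type I error.** With one result per patient, chance responses are equally likely in every arm and the test keeps its level. If each patient's two ears entered the chi-square as separate rows, the variance would be understated by a factor 1 + ρ, where ρ is the between-ear correlation of response. The error rate would be 2[1 − Φ(1.96/√(1 + ρ))]: 7.4%, 9.8% and 12.1% for ρ = 0.2, 0.4 and 0.6. Simulation at a 25% response rate agrees (7.5%, 10.0%, 12.3%).

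**The case against.** **The threshold may be a patient-level description.** In the synopsis, ≥30 dBHL sits in parentheses after the test name, where the other measures carry their score range, and it closely repeats the inclusion criterion. Read that way, every eligible patient already meets it and the SAP has lost nothing. This reading is possible. But the text sits inside the responder measure and is not a score range, so it may equally limit which thresholds count. Even on the patient-level reading, the SAP counts gains at frequencies with no hearing loss and should say that this is intended.

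**The change is visible.** Section 9 prints both wordings, so nothing is hidden. Only the reason is missing.

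**Other PTA analyses are planned.** The SAP has stricter exploratory responder rules (two adjacent frequencies, or 20 dB at one) and a continuous repeated-measures model. They reduce reliance on a single 10 dB shift, but they neither change the primary rule nor name the ear.

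**A floor does not remove noise.** It only removes sites below 30 dBHL. Retest shifts at qualifying frequencies still count.

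**Two stronger readings are tempting, and the documents support neither.** A reader might infer that the SAP counts a shift at any of six ear-frequency sites. It does not say so: the ear is left open, and 8.3.1.1 speaks of the ear value in the singular. A reader might also infer an inflated type I error. That needs ears as independent rows in the chi-square, which the SAP nowhere states.

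**Not all the text is available.** Only the protocol synopsis and schedule can be read, and some SAP text just before 8.3.1.1 is missing. An ear rule elsewhere cannot be excluded. The missing threshold in 5.1, 6.2.1 and 8.3.1.1 stands regardless.

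**Conclusion.** The point holds as a gap in a primary endpoint definition that should be closed. A condition that the protocol places in the responder measure is absent from every SAP statement of the primary rule, without explanation, and the ear is undefined in the text available.

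The consequence is dilution and lost power. Under the assumptions in the working, moving from one site to three costs roughly 16 to 35 percentage points of power (88.6% to 72% at SD 5 with correlated sites; 74.5% to 39.5% at SD 7 with independent sites). Six sites is the worst case. The retest SD, the correlations and the 30% true response are all assumed, so these figures show a scale and do not predict this trial's power.

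The one-site figures are not what the correction would deliver for everyone. A patient with loss at all three low frequencies keeps three sites. If the analysis already uses one ear, that patient's result does not change.

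**What to change.** Before unblinding, put one definition in SAP 5.1, 6.2.1 and 8.3.1.1, for example:

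> One result per patient. A PTA responder has a ≥10 dB improvement at 250, 500 or 1000 Hz, at a frequency with baseline ≥30 dBHL, in the affected ear, at visit [3 or 4, to be named].

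Add a prespecified rule for patients with both ears affected, for example the ear with the worse mean baseline low-frequency threshold. Use the same ear for WINT, where 8.3.1.2 leaves it equally open. Report the other ear descriptively and keep the present SAP rule as a sensitivity analysis. In section 9, give the reason for any remaining difference from the protocol.

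**Cost.** SAP wording and programming; the planned audiometry already supplies the thresholds. Confirm that the case report form identifies the affected ear, since the SAP mentions it only for bone conduction. If it does not, fix a derivation from baseline data before unblinding. Response rates will fall in every arm, and gains seen only at near-normal frequencies will no longer count.

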#### **Confidentiality Statement**

Version No.: Final 1.0

Sponsor Study No: SPI-1005-251

Sponsor Name: Sound Pharmaceuticals, Inc.

NLS Study Code: SPI-1005-251 Short

Short Title of Study: SPI-1005-251 (Sound Pharmaceuticals, Inc)

➢ Word recognition score using WINT at 24, 20,16, 12, 8, 4 and 0 SNR; or

Page 9 of 38

- > Improvement in the Tinnitus Functional Index (TFI); or
- Improvement in Tinnitus Loudness (TL); or
- Improvement in the Vertigo Symptoms Scale (VSS)

